### 10.2 Analysis Datasets

All eligible lesions evaluated by both the teledermatologists and the in-person dermatologist.

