#### 10.3.2 Analysis of the Primary Efficacy Endpoint(s)

To determine the agreement between in-person recommendation and the telemedicine (tele) recommendation we can calculate the number of discordant benign vs. malignant diagnoses; specifically, the number of subjects that were recommended a biopsy from the in-person dermatologist but were recommended no biopsy from the teledermatology team, and the number of subjects that were recommended no biopsy from the in-person dermatologist but biopsy by the teledermatologist team. We can calculate the Kappa coefficient as a measure of the degree of concordance or agreement with confidence intervals. We can also calculate "sensitivity" and "specificity" of the tele method assuming in-person diagnosis as the gold standard. Similarly, we can separately evaluate the agreement between in-person and: 1) dermoscopy alone; and 2) Nevisense (EIS score  $\geq 4$ ) without dermoscopy. We will also estimate the improvement (if any) of using both methods compared to one method. We expect the Kappa coefficient to be close to one, and high "sensitivity" and "specificity" (close to 1) for the SpotCheck method assuming in-person diagnosis as the gold standard.

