#### 10.3.3 Analysis of the Secondary Endpoint(s)

Secondary endpoint (1) will be a descriptive analysis of Sensitivity, Specificity, Positive Predictive Value, and Negative Predictive Value, using the histopathology results as the gold standard. We will assess potential difference or advantages in terms of: a) enhanced telemedicine diagnostic system; b) telemedicine Nevisense alone; c) telemedicine clinical + dermoscopy alone; and d) in-person dermatologist diagnosis. Sensitivity, Specificity, Positive Predictive Value, and Negative Predictive Value will be reported with an upper and lower confidence interval. Lesions with missing data will not be included in the relevant analyses (see Study Design schematic footnote 3). Participants lost to follow-up for reporting his/her biopsy results will be included in the analysis as the data required for analysis has been collected.

As another secondary endpoint, we will be evaluating the enhanced telemedicine service's impact on patient centered outcomes. Descriptive statistics for this secondary endpoint (2) (patient questionnaires, Supplement L will be presented as percentages. Study completion questionnaires may be qualitatively analyzed for themes and quantified by thematic representation across participants. Participant agreement of thematic categories will be calculated as percentages as a summary measure. Factors for stratification may include participants with a biopsy procedure and those without biopsy procedure as well as diagnosis of malignancy or benign lesion within those with biopsy. Participants with missing study completion questionnaire results due to inadequate duration of phone call will not be included.

As a final secondary endpoint (3), we will estimate the number of lesions that may benefit from the additional information of the Nevisense score to the clinical and dermoscopic exam. This estimation will be provided by the in-person dermatologist, and separately by each of the three teledermatologists (Supplement T & U). The estimates will be expressed as percentages. Any lesion with missing data in the in-person dermatologist and teledermatologist plan will not be included in analysis. Participants lost to follow-up will still be included in analysis of this endpoint as required data for this endpoint determination has been captured in the first visit.

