**10.4 Sample Size**

Number of subjects to recruit and screen is estimated to be 650 or fewer. Number of participants eligible is estimated to be 500 or fewer. Based on the previously mentioned Norwegian study, we anticipate a biopsy recommendation rate of 10% between the telemedicine and in-person evaluations. With each participant presenting with 1-3 lesions, an estimate of 1000 evaluated lesions (2 per participant on average) is possible. Assuming a biopsy recommendation 10% from this historical data, there will be likely 50 - 100 biopsies recommended and 450 - 900 lesions not recommended for biopsy.

We anticipate 2% of the sample will be lost to follow up based on historical data. Missing data is estimated at 4% based on those lost to follow up and technical error based on historical data. We anticipate 1% of participants to withdraw based on historical data. Participants who have formally withdrawn from the study will not be included in primary or secondary endpoint analysis, nor will they be included in the analysis datasets.

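### Confidence intervals are promised on a dataset of lesions, 1 to 3 per participant, but no interval method allows for several lesions from one person and the unit of analysis is not settled

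*Combined protocol and SAP*

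**What the plan says.** - **Unit.** Section 10.2 defines one analysis set: "All eligible lesions evaluated by both the teledermatologists and the in-person dermatologist". Section 10.3.2, however, describes discordance as "the number of subjects that were recommended a biopsy from the in-person dermatologist but were recommended no biopsy from the teledermatology team", plus the reverse count. No rule turns one to three lesion results into one subject result. Footnotes 2 and 4 of the Schematic of Study Design expect mixed recommendations within a participant.
- **Numbers.** Section 10.4 says "Number of participants eligible is estimated to be 500 or fewer", and that "an estimate of 1000 evaluated lesions (2 per participant on average) is possible". Section 5.1 admits people with one to three lesions.
- **Intervals.** Section 10.3.2 states "We can calculate the Kappa coefficient as a measure of the degree of concordance or agreement with confidence intervals". It also plans sensitivity and specificity against the in-person decision, but attaches no interval to them there. Section 10.3.3, with histopathology as reference, states "Sensitivity, Specificity, Positive Predictive Value, and Negative Predictive Value will be reported with an upper and lower confidence interval".
- **What is absent.** No confidence level, interval method or variance estimator is given. Clustering, within-participant correlation, robust variance and resampling by participant are not mentioned.
- **Role of the intervals.** Section 10.1 rules out hypothesis testing and describes a descriptive pilot.

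**The concern.** Lesions from one participant share skin type, risk history, one imaging visit, one in-person examination and the same teledermatology readers. Some positive correlation in whether the two methods agree, or are correct, is therefore plausible. The textbook standard error for kappa and the binomial interval for a proportion both treat each lesion as a separate independent observation. With nothing else specified, an analyst handed the 10.2 dataset is likely to use them.

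Because there is no hypothesis test, the intervals are the study's only formal statement of uncertainty. The Protocol Summary says that the pilot is meant to supply preliminary data for larger studies, so overstated precision would carry into their planning.

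**Working it through.** **Inputs from the documents.** 500 participants, 1 to 3 lesions each, mean 2, biopsy recommendation rate 10% (all 10.4); malignancy in about 2% of subjects (2.4.2).

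**Assumptions, because the documents are silent.** ICC of 0.1 to 0.5; 95% level; specificity 95% and sensitivity 90% for illustration; either exactly two lesions each, or equal thirds with one, two and three.

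**1. The plan's own figures.** 500 × 2 = 1000 lesions. At 10%, 500 lesions give 50 biopsies and 450 non-biopsies, and 1000 lesions give 100 and 900. This matches the ranges 50–100 and 450–900 in 10.4. The plan states no interval width that could be reproduced.

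**2. Simple lesion-level proportions (percent agreement, specificity against the in-person decision).** Design effect = 1 + (m_w − 1) × ICC, where m_w = Σm²/Σm. The width factor is its square root.

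- Exactly two each: m_w = 2.
- Equal thirds: m_w = (1 + 4 + 9)/(1 + 2 + 3) = 14/6 = 2.33.

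| ICC | Design effect, two each | Wider by | Design effect, equal thirds | Wider by |
|---|---|---|---|---|
| 0.1 | 1.10 | 4.9% | 1.13 | 6.5% |
| 0.3 | 1.30 | 14% | 1.40 | 18% |
| 0.5 | 1.50 | 22% | 1.67 | 29% |

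Example: specificity 95% on 900 lesions has half-width 1.96 × √(0.95 × 0.05/900) = 1.42 points. Multiplying by the two width factors gives 1.62 to 1.68 points at ICC 0.3 and 1.74 to 1.84 at ICC 0.5. This uses m_w for all lesions, so it slightly overstates the effect for the non-biopsy subset.

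**3. Sensitivity against the in-person decision.** Only the roughly 100 biopsy-recommended lesions enter, and few participants contribute more than one. Take two lesions each, p = 0.1, and r as the ICC of biopsy status. The probability that both lesions are positive is p11 = p² + r·p(1 − p), the probability of exactly one is p1 = 2(p − p11), and m_w = (4·p11 + p1)/(2·p11 + p1).

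- r = 0: p11 = 0.010, p1 = 0.180, m_w = 0.22/0.20 = 1.10.
- r = 0.5: p11 = 0.055, p1 = 0.090, m_w = 0.31/0.20 = 1.55.

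At an ICC of 0.3 for correctness, the design effect is 1 + 0.10 × 0.3 = 1.03 to 1 + 0.55 × 0.3 = 1.165, so intervals are about 1.5% to 8% wider. A sensitivity of 90% on 100 lesions has half-width 5.88 points, which becomes about 5.97 to 6.35.

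**4. Kappa.** There is no simple design effect, so this was simulated: 500 participants, one to three lesions with equal probability, 10% biopsy rate for each method, kappa about 0.65, 2000 replicates. A participant effect was shared by the underlying suspicion and by each method's error.

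| Shared participant effect | True SE / usual SE | Coverage of nominal 95% |
|---|---|---|
| 0 | 1.00 | 94.6% |
| 0.3 | 1.00 | 95.2% |
| 0.5 | 1.03 | 94.2% |
| 0.8 | 1.08 | 93.9% |
| 1.0 (extreme) | 1.54 | 79.5% |

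Further simulations of this type gave 1.07 to 1.12 with strong sharing (coverage 91% to 92%). At kappa about 0.84 the ratio was 0.99 to 1.03. One set at kappa 0.58 reached 1.21 (coverage 89%) at its strongest setting. Short of that end of the scale, about 0% to 12% is a fair range.

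**5. Secondary endpoint 1.** Histopathology exists only for biopsied lesions, so the base is about 50 to 100 lesions. Malignancy in 2% of 500 subjects is about 10 people. Small counts, more than clustering, determine the uncertainty here.

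**The case against.** The strongest objection is that the plan commits no error: it names no interval method, and a clustered interval would comply with every sentence in it. That is right, and this point is therefore an omission. A reader might infer that ordinary intervals are specified and already overstate precision, but the documents do not say so.

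Second, if 10.3.2 truly intends one result per subject, clustering disappears for the primary endpoint. This stands as a possibility. However, 10.2 defines only lesions and no combining rule exists, so kappa most naturally falls on lesions. Either way the plan has to say which.

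Third, the documents offer no evidence on the size of the correlation. A reader might infer near all-or-none clustering from setting the 10% of subjects biopsied (2.4.1) beside 10% of 1000 lesions (10.4). That does not hold. Section 10.4 gives 50 to 100 biopsies, and 50 biopsies in 50 of 500 participants needs no clustering. These are also rounded planning figures. And correlation of biopsy status is not what widens an interval for agreement or specificity; that depends on correlation of agreement or correctness.

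Fourth, no test, margin or sample-size decision uses these intervals, and 10.3.2 expects kappa close to one, where the simulated effect is small. Both facts limit the consequence but do not remove the gap.

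**Conclusion.** The point holds as an omission of modest size. About two lesions per participant enter the analysis set, intervals are promised, and neither the independent unit nor an interval method that respects it is stated. Independence-based intervals on lesions would be too narrow whenever the within-participant correlation is positive. They would be correct if it is zero, if each person brings one lesion, or if the analysis is per participant.

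Assuming ICC 0.1 to 0.5, intervals for simple lesion-level proportions should be about 5% to 29% wider. The kappa standard error is short by about 0% to 12%, apart from extreme sharing. Sensitivity against the in-person decision is affected by about 1.5% to 8% at ICC 0.3.

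A reader might carry the effective sample sizes for proportions (1000/1.13, 1000/1.40 and 1000/1.67, or about 882, 714 and 600 lesions) over to kappa or to the histopathology endpoint. That is not supported: kappa responds less, and the histopathology endpoint starts from about 50 to 100 lesions. The matter should be settled before analysis, but it does not threaten the design.

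**What to change.** In 10.3.2 and 10.3.3:

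1. State that the lesion is the unit of analysis and the participant the independent unit. Restate the discordance counts by lesion, or give the rule for combining lesions if a subject-level count is also wanted.
2. State the confidence level, and obtain intervals for agreement, kappa, sensitivity, specificity, both predictive values and their differences with participant-level clustering. Either a bootstrap that resamples participants with all their lesions, or a cluster-robust variance, will do.
3. State a fallback for estimates at or near 0 or 1, or where cancers are few. If no cancer is missed, every bootstrap sample returns 100% and the interval collapses. Report an exact or Wilson interval there. As a conservative sensitivity check, repeat it with one lesion per participant or with the number of participants as denominator. A fallback that needs an estimated ICC would not work with about 10 people with cancer.

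The cost is a few sentences in the plan, a few lines of code and somewhat wider intervals. No extra data or participants are needed.

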### **2.3 Rationale**

Detection of melanoma at its earliest stages is associated with high surgical cure rates, without the need for additional, potentially toxic and expensive systemic therapies. Rural and other medically underserved communities have higher rates of melanoma mortality that is associated with reduced access to dermatologic diagnostic services. We aim to study the effectiveness of an augmented telemedicine diagnostic platform for melanoma and other skin cancers that can potentially be deployed in pharmacies and urgent care centers that would be more available in rural communities than dermatologist offices.

The study will evaluate participant-selected lesions of adults in the New York City metropolitan area to simulate the walk-in clinic or pharmacy community setting. The control is an in-person evaluation by a community dermatologist, the current gold

standard. We aim to assess the sensitivity and specificity of the platform compared to the in-person dermatological examination in the diagnosis of melanoma and other skin cancers. Since the Nevisense evaluation is one component of the platform, and the current FDA approval is for it to be used in dermatologist offices to aid in biopsy decisions, we will also examine the degree to which teledermatologists can use the clinical and dermoscopy images to evaluate whether each study lesion would have been appropriate for the Nevisense evaluation had they seen the patient in-person. Finally, we will examine whether the combined teledermoscopy/clinical images plus Nevisense will have greater sensitivity and specificity to diagnose melanoma and other skin cancers than either approach alone.

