## **6 Study Agent (Study drug, device, biologic, vaccine etc.) and/or Procedural Intervention**

### **6.1 Study Agent(s) and Control Description**

The Procedural Intervention is the telemedicine evaluation; the Control is the in-person dermatologist evaluation. The Procedural Intervention includes 3 components:

- 1) Clinical images (from 6 inches, 12 inches, and 24 inches from the lesion) captured and uploaded to the subject's EPIC EMR medical chart as a research note or captured by the Barco Demetra and uploaded to its associated software
- 2) Close up clinical and dermoscopic imaging of the lesion(s) of concern with a dermoscopy camera (DermLite Cam, 3Gen, San Juan Capistrano, CA or Barco Demetra, Barco NV, Kortrijk, BE)
- 3) An electrical impedance spectroscopy measurement of said lesions using the Nevisense 3.0 device (Scibase, Sundbyberg Sweden)
- 4) Store-and-forward telemedicine evaluation of the imaging and Nevisense measurements by a team of 3 dermatologists.

The goal is to determine whether the lesion(s) of concern to the participant is a benign skin growth, or a possible skin cancer in need of a biopsy to definitively establish the diagnosis. The Nevisense 2.0 device is FDA cleared for use in dermatologists' offices. The Nevisense 2.0 device will not be used in this study. Rather, the updated, not yet approved Nevisense 3.0 device will be used. The 3.0 version consists of a software update and provides a simpler a workflow that no longer requires a reference measurement from the subject's normal skin, thus saving time. The 3.0 device has no change in the hardware.. Verbal FDA clearance occurred in January 2020 and formal FDA clearance is expected in April 2020. Regardless of approval, the proposed use of Nevisense 3.0 in a telemedicine setting for this study represents an off-label use of the device.

It measures electrical impedance of the lesion with single-use electrodes (i.e. changed between each participant). The device has a hardware probe that takes the measurement in <10 seconds and a software component that displays the data on the control unit screen.

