In addition to the DermLite Cam images, a study specific camera or EPIC HAIKU will be used to acquire 3 clinical images of <5 seconds per lesion (from 6 inches away, 12 inches away, and 18 inches away). Images will be stored in the patient's medical record in Epic, to which the teledermatology team has access. Clinical images taken through Epic Haiku or the study specific camera will not be stored elsewhere. Images taken with the study specific camera will be deleted from the camera once images are uploaded to EPIC.

The Barco Demetra device will be used to acquire 3 images of <5 seconds per lesion (one clinical, one polarized dermoscopic, and one non-polarized dermoscopic) as well as 3 additional clinical images of <5 seconds per lesion (from 6 inches away, 12 inches away, and 18 inches away). Images will be stored in the authenticated and data-encrypted Demetra Cloud accessible via the web by the telemedicine team in the NYU Department of Dermatology Pigmented Lesion Clinic. The telemedicine dermatology team will review the images using this dedicated cloud software. Clinical and dermoscopic images taken by the Barco Demetra device will not be stored elsewhere.

Lesions with bleeding or ulceration will only have a clinical image taken and not have a dermoscopic image taken.

The telemedicine dermatology team will consist of [name], [name], and [name], who are all pigmented lesion experts. They will be listed as co-investigators. They will submit independent, blinded to each other, diagnoses for each lesion on REDCap. If at least one teledermatologist believes the lesion to be a malignant diagnosis, the lesion will be recommended for biopsy. If the participant has not already had the lesion biopsied by the in-person recommendation, the participant will be told this concern for malignancy and telemedicine recommendation for biopsy.

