## 10 Statistical Considerations

### 10.1 Statistical Hypotheses

Primary endpoint:

We will not perform hypothesis testing in this pilot study; we will use descriptive statistics and summarize preliminary evidence from this pilot study.

Secondary endpoints

We will not perform hypothesis testing in this pilot study.

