## **10.5 Measures to Minimize Bias**

### **10.5.1 Enrollment/Randomization/Masking Procedures**

**10.5.2** Subjects will be self-enrolled into the study by viewing an advertisement and making an appointment for enrollment at the DCSU. Enrollment procedures include eligibility verification and informed consent confirmation with signature. The in-person dermatologist (control arm) and telemedicine team (intervention arm) will each be blinded to the other's management recommendation. The in-person dermatologist will be blinded to the Nevisense score. Additionally, the teledermatologist team of 3 physicians will be masked to each other's management plan. If one teledermatologist is absent (due to vacation, illness etc.) and cannot make their recommendations, a minimum of 2 teledermatologists is satisfactory to make a consensus. If any teledermatologist recommends biopsy, the team recommendation will be biopsy. Periodic reviews of teledermatology diagnoses by the teledermatology team will be held in order to improve quality control during the study. **Evaluation of Success of Blinding**

Not applicable

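### Section 10.3.2 sets an any-of-three telemedicine panel against one in-person reader, so its discordance, sensitivity and specificity mix reader count with modality; per-reader results from reads already recorded are not planned

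*Combined protocol and SAP*

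**What the plan says.** - **Intervention.** Section 6.1 defines telemedicine evaluation as done "by a team of 3 dermatologists". The decision rule in Section 6.1.4 is "If at least one teledermatologist believes the lesion to be a malignant diagnosis, the lesion will be recommended for biopsy", and Section 10.5.1 repeats it: "If any teledermatologist recommends biopsy, the team recommendation will be biopsy". If a reader is absent, "a minimum of 2 teledermatologists is satisfactory to make a consensus", so some lesions get two reads and others three.
- **Comparator.** Section 2.3: "The control is an in-person evaluation by a community dermatologist". Sections 3.2 and 4.1 likewise describe one in-person assessment.
- **Primary analysis.** Section 10.3.2 plans the two directional discordant counts, kappa with confidence intervals, and sensitivity and specificity with the in-person decision as the standard. It also plans agreement for dermoscopy alone and Nevisense alone. It states "We expect the Kappa coefficient to be close to one" and expects sensitivity and specificity near 1 as well.
- **Individual reads.** Section 6.1.4, on the three teledermatologists: "They will submit independent, blinded to each other, diagnoses for each lesion on REDCap". Section 10.3.3 reports secondary endpoint 3 reader by reader, but Section 10.3.2 does not do this for the primary endpoint.
- **Status.** Section 10.1: "We will not perform hypothesis testing in this pilot study; we will use descriptive statistics".

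**The concern.** Section 4.2.1 says the study is to describe the discrepancy between telemedicine and in-person evaluation. A panel that is positive when any member is positive will recommend more biopsies than one reader of the same skill and threshold, whatever the medium. The planned tables would then show many telemedicine-only biopsies and few in-person-only ones. That pattern invites the reading that remote images plus Nevisense are more sensitive and less specific, when some or all of it may come from three readers against one. The dermoscopy-alone and Nevisense-alone analyses change the information used; they are not designed to isolate reader count. A descriptive study is not protected by the absence of a test, because the description itself is what would be misattributed.

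**Working it through.** **Inputs**

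- Three readers (6.1), any-positive rule (6.1.4, 10.5.1), minimum two (10.5.1), one in-person reader (2.3).
- Biopsy rate p: 8% of lesions in the Norwegian pharmacy service (2.1). Section 10.4 uses 10%, citing the same service. Both are used below.
- 1000 lesions, i.e. 500 participants × 2 (10.4). I count lesions, the unit in 10.2; 10.3.2 words its discordant counts as subjects.
- Pairwise kappa κ between any two readers: **assumed**, since the documents give none. Range 0.4 to 0.95.
- No modality effect: imposed on purpose, so that whatever remains is due to the panel rule.

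**The plan's own figures.** 10% × 500 = 50 and 10% × 1000 = 100 biopsies; 90% × 500 = 450 and 90% × 1000 = 900 without. These match Section 10.4. The kappa expectation has no inputs and cannot be reproduced.

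**Direction, without a model.** Every lesion that one teledermatologist calls positive is also positive for the team. Team sensitivity is therefore at least that of its most sensitive member, and team specificity at most that of its least specific member.

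**One telemedicine reader (p = 0.08, κ = 0.6).** Both positive: p² + κp(1−p) = 0.0064 + 0.6 × 0.0736 = 0.0506. Each discordant cell: (1−κ)p(1−p) = 0.4 × 0.0736 = 0.0294, or 29 and 29 per 1000. Sensitivity 0.0506/0.08 = 63%; specificity 1 − 0.0294/0.92 = 97%.

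**Any of m readers.** One-factor normal model for exchangeable readers. A reader's positive probability given the lesion factor z is q(z) = Φ((√ρ·z − t)/√(1−ρ)), with t = Φ⁻¹(1−p) and ρ solved so that E[q²] = p² + κp(1−p). Then:

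- team rate = E[1−(1−q)^m]
- both positive = E[q{1−(1−q)^m}]

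Per 1000 lesions at p = 0.08:

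| κ (assumed) | Telemedicine | Both | Tele only | In-person only | Sens. | Spec. | Tele rate |
|---|---|---|---|---|---|---|---|
| 0.6 | one reader | 50.6 | 29.4 | 29.4 | 63% | 97% | 8.0% |
| 0.6 | any of three | 66.6 | 61.2 | 13.4 | 83% | 93% | 12.8% |
| 0.8 | one reader | 65.3 | 14.7 | 14.7 | 82% | 98% | 8.0% |
| 0.8 | any of three | 74.3 | 28.7 | 5.7 | 93% | 97% | 10.3% |

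Sensitivity = both/80; specificity = 1 − (tele only)/920; rate = (both + tele only)/1000. With two readers at κ = 0.6, the team rate is 10.9% and sensitivity 77%, so an absence changes the operating point.

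**Kappa, κ = 0.6, any of three.** Observed agreement = 1 − (61.2 + 13.4)/1000 = 0.9254. Chance agreement = 0.08 × 0.1278 + 0.92 × 0.8722 = 0.8126. Kappa = (0.9254 − 0.8126)/(1 − 0.8126) = 0.60, the same as for one reader.

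**Range at p = 10%, one reader → any of three**

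| κ (assumed) | Sensitivity | Specificity | Kappa | Tele rate |
|---|---|---|---|---|
| 0.4 | 0.46 → 0.72 | 0.94 → 0.87 | 0.40 → 0.42 | 10% → 19% |
| 0.6 | 0.64 → 0.84 | 0.96 → 0.92 | 0.60 → 0.60 | 10% → 16% |
| 0.8 | 0.82 → 0.93 | 0.98 → 0.96 | 0.80 → 0.79 | 10% → 13% |
| 0.9 | 0.91 → 0.97 | 0.99 → 0.98 | 0.90 → 0.90 | 10% → 11% |

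At κ = 0.95, team kappa is 0.95. A team kappa of 0.90 needs pairwise kappa of about 0.905. A beta-binomial model in place of the normal one moves these any-of-three figures by less than 0.015.

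**A different dependence.** If telemedicine errors are independent given the in-person decision, the rule does lower kappa. A single reader at 0.90/0.95 becomes 1 − 0.1³ = 0.999 and 0.95³ = 0.857, and kappa falls from 0.74 to 0.55 at p = 10%. The documents do not say which dependence applies.

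**The case against.** **The panel is the intervention.** Sections 4.2.1 and 6.1 define the endpoint and the service at team level, so extra sensitivity bought with lower specificity is a true property of the platform. This stands, and the team estimate should remain primary. It does not tell a reader how much of the discrepancy comes from using three readers.

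**Modality can already be isolated.** Section 3.2, objective 1(i), has the in-person dermatologist re-read the telemedicine data at study end. That holds reader count and expertise fixed. A reader might infer that the plan has no means of separating modality from reader count; that would be wrong. The gap is that Section 10 never uses the re-read, and that it provides no benchmark for variation between readers.

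**The kappa expectation.** A reader might infer that the panel rule puts a kappa near one out of reach. The documents do not support this. With exchangeable readers, team kappa stays within about 0.02 of single-reader kappa for κ of 0.4 or more, and a low value would come from low reader agreement, on which the documents are silent. The expectation is unsupported, not shown to be unattainable.

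**Nothing fails if kappa is 0.6 to 0.8.** Correct: there is no test and no threshold, and Section 10.3.1 allows that telemedicine may outperform in-person evaluation against pathology. That allowance does fit poorly with expecting near-perfect agreement.

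**Conclusion.** The point holds as a low-cost improvement to the primary analysis. The discordant counts, sensitivity and specificity in Section 10.3.2 combine reader count and decision rule with modality, and no planned analysis in Section 10 separates them. The direction follows from the rule alone. The size rests on assumed reader agreement, on readers sharing one biopsy rate, and on exchangeable errors. At an 8% rate and pairwise kappa 0.6, sensitivity rises by about 20 percentage points, specificity falls by about 3 to 4, and discordance goes from 29 vs 29 to 61 vs 13 per 1000. At pairwise kappa 0.8, discordance goes from 15 vs 15 to 29 vs 6. The effect shrinks towards nothing as reader agreement approaches 1. The kappa expectation needs a stated basis or should go; it would be met if pairwise agreement were about 0.9 or higher.

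**What to change.** Keep team versus in-person as the primary result and add to Section 10.3.2, from reads already entered in REDCap:

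1. Discordant counts, kappa, sensitivity and specificity for each teledermatologist against the in-person dermatologist.
2. Pairwise kappa among the teledermatologists, as the benchmark for ordinary reader variation.
3. The team result separately for two-reader and three-reader lesions.

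Carry the re-read of Section 3.2, objective 1(i), into Section 10 as the within-reader comparison of modality. Delete the kappa expectation, or state the reader agreement it assumes.

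The cost is a few table rows, and items 1 to 3 need no new reads or participants. Before relying on item 1, confirm that the teledermatologist form (Supplement U, not in the documents reviewed) holds each reader's biopsy call and not only a diagnosis. One limit remains: the teledermatologists are pigmented-lesion experts (6.1.4) and the comparator is a community dermatologist (2.3), so per-reader results remove the reader-count difference but not the difference in expertise. Only the re-read removes both.
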